8.2 SAFETY AND OTHER ASSESSMENTS

Patients will be screening for allergy to or contraindications to study medication. If they meet criteria and consent for the study, then each patient will be monitored for safety in multiple forms. For each patient,

vital signs are monitored in the operating room and during recovery until discharge as part of routine clinical care. Electrocardiogram monitoring will also be continuously ongoing in the operating room as part of routine clinical care. Assessment of adverse events throughout hospital stay will be done by review of charts and discussion with other members involved in patient care.

8.3 ADVERSE EVENTS AND SERIOUS ADVERSE EVENTS

8.3.1 DEFINITION OF ADVERSE EVENTS (AE)

Adverse event means any untoward medical occurrence associated with the use of an intervention in humans, whether or not considered intervention-related.

8.3.2 DEFINITION OF SERIOUS ADVERSE EVENTS (SAE)

An adverse event (AE) or suspected adverse reaction is considered "serious" if, in the view of the investigator, it results in any of the following outcomes: death, a life-threatening adverse event, inpatient hospitalization or prolongation of existing hospitalization, a persistent or significant incapacity or substantial disruption of the ability to conduct normal life functions, or a congenital anomaly/birth defect. Important medical events that may not result in death, be life-threatening, or require hospitalization may be considered serious when, based upon appropriate medical judgment, they may jeopardize the participant and may require medical or surgical intervention to prevent one of the outcomes listed in this definition. Examples of such medical events include allergic bronchospasm requiring intensive treatment in an emergency room or at home, blood dyscrasias or convulsions that do not result in inpatient hospitalization, or the development of drug dependency or drug abuse.

8.3.3 CLASSIFICATION OF AN ADVERSE EVENT

8.3.3.1 SEVERITY OF EVENT

For adverse events (AEs) not included in the protocol defined grading system, the following guidelines will be used to describe severity.

- **Mild** – Events require minimal or no treatment and do not interfere with the participant's daily activities.
- **Moderate** – Events result in a low level of inconvenience or concern with the therapeutic measures. Moderate events may cause some interference with functioning.
- **Severe** – Events interrupt a participant's usual daily activity and may require systemic drug therapy or other treatment. Severe events are usually potentially life-threatening or incapacitating. Of note, the term "severe" does not necessarily equate to "serious".

8.3.3.2 RELATIONSHIP TO STUDY INTERVENTION

All adverse events (AEs) must have their relationship to study intervention assessed by the clinician who examines and evaluates the participant based on temporal relationship and her clinical judgment. The degree of certainty about causality will be graded using the categories below. In a clinical trial, the study product must always be suspect.

- **Related** – The AE is known to occur with the study intervention, there is a reasonable possibility that the study intervention caused the AE, or there is a temporal relationship between the study intervention and event. Reasonable possibility means that there is evidence to suggest a causal relationship between the study intervention and the AE.
- **Not Related** – There is not a reasonable possibility that the administration of the study intervention caused the event, there is no temporal relationship between the study intervention and event onset, or an alternate etiology has been established.

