4 STUDY DESIGN

4.1 OVERALL DESIGN

- Central Objective To examine patients reported pain levels or narcotic usage between pre-incision versus post-incision subcutaneous infiltration of 4-5mL 0.25% Bupivacaine after a robotic/laparoscopic-assisted sacrocolpopexy.

Research Plan:

- Randomized, controlled, single-blinded study

Setting of the study:

- Operating room of patients undergoing robotic/laparoscopic sacrocolpopexy

Participants:

- Patients aged 18 years old and above who are scheduled to undergo robotic/laparoscopic-assisted sacrocolpopexy (with or without hysterectomy and with or without midurethral sling)

Randomization Scheme

- Randomization will be accomplished using the Biostatistics Randomization Management System
- 1:1 Randomization, permuted blocks
- Subjects will be randomized using a computer generated table into one of two groups:
 - Arm one: subcutaneous infiltration pre-incision
 - Arm two: subcutaneous infiltration post-incision
- Surgeons will be notified by e-mail of their patient allocation on day of surgery

Pre-surgery

- Consent will be obtained and the patient will be given a Brief Pain Inventory Questionnaire to complete. The Brief Pain Inventory Questionnaire is a validated medical questionnaire to measure pain. The questionnaire measures the patient's pain intensity and the amount of interference the pain has on their being able to function in their daily living.
- Intervention or experimental aspect of the study
 - General anesthesia will be given as per standard protocol
 - Preoperative pain medication will be ordered for each patient as per standard enhanced recovery protocol
 - Operative Time: Generally total of 180 – 300 minutes
 - Total dose of 0.25% Bupivacaine injection:
 - 8-10 mm incisions x 5 incisions = 20-25 mL (4-5 mL each)
 - 20-25mL of 0.25% Bupivacaine distributed over 5 trocar sites (4-5mL per incision)
 - Skin closure: subcutaneous closure with monofilament absorbable suture with 4-0 absorbable suture and fascia closure of the umbilical port site with #0 delayed absorbable suture and skin closure with 4-0 absorbable suture

- Pre-incision arm: Marcaine (bupivacaine) injected in the umbilical port site subcutaneously, while in the other 4 sites injection under direct visualization
- Post-incision arm: local anesthetic infiltrated subcutaneously at the end of the procedure after trocar removal and after skin closure with suture

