8.4 UNANTICIPATED PROBLEMS

8.4.1 DEFINITION OF UNANTICIPATED PROBLEMS (UP)

The Office for Human Research Protections (OHRP) considers unanticipated problems involving risks to participants or others to include, in general, any incident, experience, or outcome that meets **all** of the following criteria:

- Unexpected in terms of nature, severity, or frequency given (a) the research procedures that are described in the protocol-related documents, such as the Institutional Review Board (IRB)-approved research protocol and informed consent document; and (b) the characteristics of the participant population being studied;
- Related or possibly related to participation in the research (“possibly related” means there is a reasonable possibility that the incident, experience, or outcome may have been caused by the procedures involved in the research); and
- Suggests that the research places participants or others at a greater risk of harm (including physical, psychological, economic, or social harm) than was previously known or recognized.

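### Section 8.3.3.2: the Related and Not Related categories overlap and timing alone suffices for Related, so in a trial that randomizes injection time the grades can differ by arm for reasons other than drug effect

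*Combined protocol and SAP*

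**What the plan says.** Section 8.3.3.2 asks the examining clinician to grade each AE "based on temporal relationship and her clinical judgment", and adds that the product must always be under suspicion. There are two grades.

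- *Related* has three alternatives. The first is "The AE is known to occur with the study intervention". The other two are that "there is a reasonable possibility that the study intervention caused the AE, or there is a temporal relationship between the study intervention and event".
- *Not Related* also has three alternatives. The first is that a reasonable possibility of causation is absent. The other two are that "there is no temporal relationship between the study intervention and event onset, or an alternate etiology has been established".

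The alternatives within each grade are joined by *or*. No rule says which grade applies when both are met.

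Section 4.1 sets the two injection times. In one arm the drug is given before the incisions are made. In the other, the plan has "local anesthetic infiltrated subcutaneously at the end of the procedure after trocar removal and after skin closure with suture".

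The same section gives an operative time of generally 180-300 minutes. The surgeon knows the arm (section 6.3), and the anesthesia team is told when the drug is injected (section 6.1.2).

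**The concern.** A two-category scale should give each event one grade. Here an event can satisfy both definitions, and being close in time to the injection is by itself enough for *Related*.

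In most trials this would be a loose definition that affects both arms alike. Here injection time is the randomized factor, so for anything that happens during surgery the temporal clause largely tracks the arm. A clinician who relies on it can grade an event *Related* in the pre-incision arm. For the same event before injection in the post-incision arm, that clause is not available. The documents do not say that the person grading is unaware of the arm.

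At stake is whether the recorded grade means the same thing in both arms when someone reads it by arm.

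**Working it through.** No figure in the plan needs reproducing. The check is on the logic of section 8.3.3.2, using its four elements:

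- K: the event is known to occur with the intervention
- R: there is a reasonable possibility of causation
- T: there is a temporal relationship
- A: an alternate etiology is established

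As written:

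- *Related* = K or R or T
- *Not Related* = (not R) or (not T) or A

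**Overlap.** Four true/false elements give 2 x 2 x 2 x 2 = 16 combinations.

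- *Related* only: R and T true, A false, K either way. 2 combinations.
- *Not Related* only: K, R and T all false, A either way. 2 combinations.
- Neither: impossible, because failing *Not Related* requires R true, which satisfies *Related*. 0 combinations.
- Both: 16 - 2 - 2 = 12 combinations.

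One may object that a reasonable possibility without a temporal relationship (R true, T false) is incoherent. Removing those 4 combinations, all of which meet both definitions, leaves 12, of which 12 - 4 = 8 still meet both. These are counts of logical cases, and some are clinically unlikely.

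**By arm, for an event during surgery.** Two assumptions apply. An event after the injection counts as having a temporal relationship, a term the plan does not define further. An event before the injection cannot have been caused by it.

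| | Pre-incision arm, after injection (T true) | Post-incision arm, before injection (T and R false) |
|---|---|---|
| *Related* met | always | only if K |
| *Not Related* met | if R is false or A is true | always |
| Both met | 6 of 8 combinations of K, R, A | 2 of 4 combinations of K, A |
| One grade only | 2 of 8, *Related* | 2 of 4, *Not Related* |

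For event types not known to occur with bupivacaine (K false), *Related* is always available in the first column and never in the second. For known effects (K true), *Related* is available in both. Section 2.3.1 lists hypotension, cardiac arrest and methemoglobinemia among the known risks. A wholly clean split needs K false, R true in the pre-incision arm, and A false. There the event is *Related* only in one arm and *Not Related* only in the other.

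**Where the grade is used.**

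- Section 8.3.4 documents all AEs whatever their relationship and collects time of onset, so capture is unaffected.
- Section 8.3.6 requires serious AEs to be reported whether or not related, with its own assessment of reasonable possibility.
- Section 8.4.1 also has its own test for unanticipated problems, namely that "there is a reasonable possibility that the incident, experience, or outcome may have been caused by the procedures involved in the research".
- Section 9.4.4 plans no comparison of related AEs.
- Section 7.1 asks, for the first ten patients, which arm they were in, when the reaction occurred and whether it was to the study drug. Halting recruitment depends on the answers.
- Section 10.1.6 has the medical monitor review safety on each arm every 6 months.

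The last two turn on attribution or arm, and the grade can enter there.

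**The case against.** The strongest defense is that the wording defect has little reach. AE capture and serious AE reporting ignore the grade. Expedited decisions rest on reasonable possibility. No test of related AEs is planned. Section 8.4.4 describes the monitor's report in terms of anticipated safety events and actions taken, without mentioning counts by relatedness. All of this stands, and it limits the consequence.

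A second argument is that clinical judgment, together with the instruction to suspect the product, resolves doubtful cases. That helps in part. The instruction leans toward *Related*, but it is not a tie-break rule, and an established alternate etiology still satisfies *Not Related*.

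A third argument is that grading an event before injection as *Not Related* is causally right. It is. The fault lies in timing alone being enough for *Related*, and in the lack of a precedence rule.

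A reader might also infer that sections 8.3.3.2 and 8.4.1 contradict each other. They do not strictly do so. Section 8.4.1 concerns the research and its procedures, and section 8.3.3.2 concerns the study intervention. The differing tests are a reason to align the wording, not proof of error.

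**Conclusion.** The point holds as a defect in a stated rule. The two grades are not mutually exclusive (12 of 16 logical combinations meet both), no precedence is given, and a temporal relationship alone suffices for *Related*. Because the injections are separated by roughly the length of the operation, grades of intraoperative events can be inconsistent and can differ by arm for reasons other than drug effect.

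The reach is limited to the recorded grade and to any by-arm safety review or tabulation that uses it. Endpoints, AE capture and serious AE reporting are not touched.

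A reader might go further and conclude that the same intraoperative event necessarily becomes *Related* in one arm and *Not Related* in the other, so that related AEs must be in excess before incision. The documents do not support that. Many events can be graded either way in the pre-incision arm. Known bupivacaine effects such as hypotension can meet *Related* even before a post-incision injection. The clinician also exercises judgment. The documents give no rate of intraoperative AEs and no indication of how literally the clause would be applied, so the size of any imbalance cannot be derived.

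**What to change.** In section 8.3.3.2:

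- Define *Related* as a reasonable possibility that the intervention caused the event. The section already explains that term, and sections 8.3.6 and 8.4.1 already use it.
- State that timing relative to injection and known effects of the drug are considered, but that timing is not sufficient alone.
- Define *Not Related* as the exact complement: no such reasonable possibility.

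In section 9.4.4:

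- Tabulate all AEs by arm from a common start, regardless of relatedness, and show onset relative to injection. The start should be no later than the pre-incision injection (induction of anesthesia, for example), so that an immediate reaction is not missed.
- Present relatedness descriptively only. Even after rewording, events before injection in the post-incision arm will properly be *Not Related*, so the grade is not a fair basis for comparing arms.

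The cost is wording in two sections. All AEs and their onset times are already collected under section 8.3.4. The documents do not state that injection time is recorded on the case report form, so one field may be needed. A small downside is that fewer events may be graded *Related* than under the current wording. The table of all AEs keeps those events visible.

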8.3.3.3 EXPECTEDNESS

The Principal Investigator and all other investigators a part of the study will be responsible for determining whether an adverse event (AE) is expected or unexpected. An AE will be considered unexpected if the nature, severity, or frequency of the event is not consistent with the risk information previously described for the study intervention.

8.3.4 TIME PERIOD AND FREQUENCY FOR EVENT ASSESSMENT AND FOLLOW-UP

The occurrence of an adverse event (AE) or serious adverse event (SAE) may come to the attention of study personnel during study visits and interviews of a study participant presenting for medical care, or upon review by a study monitor.

All AEs including local and systemic reactions not meeting the criteria for SAEs will be captured on the appropriate case report form (CRF). Information to be collected includes event description, time of onset, clinician's assessment of severity, relationship to study product (assessed only by those with the training and authority to make a diagnosis), and time of resolution/stabilization of the event. All AEs occurring while on study must be documented appropriately regardless of relationship. All AEs will be followed to adequate resolution.

Any medical condition that is present at the time that the participant is screened will be considered as baseline and not reported as an AE. However, if the study participant's condition deteriorates at any time during the study, it will be recorded as an AE.

Changes in the severity of an AE will be documented to allow an assessment of the duration of the event at each level of severity to be performed. AEs characterized as intermittent require documentation of onset and duration of each episode.

[name], co-investigator, will record all adverse events with start dates occurring any time after informed consent is obtained until 7 (for non-serious AEs) or 30 days (for SAEs) after the last day of study participation. At each study visit, the investigator will inquire about the occurrence of AE/SAEs since the last visit. Events will be followed for outcome information until resolution or stabilization.

8.3.5 ADVERSE EVENT REPORTING

Adverse events will be reported to the independent medical monitor. The independent medical monitor will record all serious and non-serious adverse events and this will be reported to the principal investigator that occurs within the 2 weeks of the study time length.

8.3.6 SERIOUS ADVERSE EVENT REPORTING

The study clinician will immediately report any serious adverse event, whether or not considered study intervention related, including those listed in the protocol or investigator brochure and must include an assessment of whether there is a reasonable possibility that the study intervention caused the event. Study endpoints that are serious adverse events (e.g., all-cause mortality) must be reported in accordance with the protocol unless there is evidence suggesting a causal relationship between the study intervention and the event (e.g., death from anaphylaxis). In that case, the investigator must immediately report the event.

All serious adverse events (SAEs) will be followed until satisfactory resolution or until the site investigator deems the event to be chronic or the participant is stable.

The co-investigator will be responsible for notifying the Food and Drug Administration (FDA) of any unexpected fatal or life-threatening suspected adverse reaction as soon as possible, but in no case later than 7 calendar days after the initial receipt of the information. In addition, the investigator must notify FDA and all participating investigators in a safety report of potential serious risks, from clinical trials or any other source, as soon as possible, but in no case later than 15 calendar days.

8.3.7 REPORTING EVENTS TO PARTICIPANTS

If any adverse event meets definition of an unanticipated problem that results in a consent form modification, subjects will be notified via the re-consenting process.

8.3.8 EVENTS OF SPECIAL INTEREST

Not applicable

8.3.9 REPORTING OF PREGNANCY

Not applicable

8.4 UNANTICIPATED PROBLEMS

8.4.1 DEFINITION OF UNANTICIPATED PROBLEMS (UP)

The Office for Human Research Protections (OHRP) considers unanticipated problems involving risks to participants or others to include, in general, any incident, experience, or outcome that meets **all** of the following criteria:

- Unexpected in terms of nature, severity, or frequency given (a) the research procedures that are described in the protocol-related documents, such as the Institutional Review Board (IRB)-approved research protocol and informed consent document; and (b) the characteristics of the participant population being studied;
- Related or possibly related to participation in the research (“possibly related” means there is a reasonable possibility that the incident, experience, or outcome may have been caused by the procedures involved in the research); and
- Suggests that the research places participants or others at a greater risk of harm (including physical, psychological, economic, or social harm) than was previously known or recognized.

8.4.2 UNANTICIPATED PROBLEM REPORTING

The investigator will report unanticipated problems (UPs) to the reviewing Institutional Review Board (IRB). The UP report will include the following information:

- Protocol identifying information: protocol title and number, PI's name, and the IRB project number;
- A detailed description of the event, incident, experience, or outcome;
- An explanation of the basis for determining that the event, incident, experience, or outcome represents an UP;
- A description of any changes to the protocol or other corrective actions that have been taken or are proposed in response to the UP.

To satisfy the requirement for prompt reporting, UPs will be reported using the following timeline:

- UPs that are serious adverse events (SAEs) will be reported to the IRB within 5 business days of the investigator becoming aware of the event.
- Any other UP will be reported to the IRB within 5 business days of the investigator becoming aware of the problem.
- All UPs should be reported to appropriate institutional officials (as required by an institution's written reporting procedures), the supporting agency head (or designee), and the Office for Human Research Protections (OHRP) within 30 days of the IRB decision.

8.4.3 REPORTING UNANTICIPATED PROBLEMS TO PARTICIPANTS

For unanticipated problems that result in a consent form modification, subjects will be notified via the re-consenting process. For other unanticipated problems that require reporting to participants as determined by the IRB, subjects will be as per the IRB's determination.

8.4.4 DATA AND SAFETY MONITORING PLAN

DATA AND SAFETY MONITORING PLAN (DSMP)

In accordance with federal guidelines, this study requires a DSMP. The PI has identified an independent Medical Monitor ([name]) with expertise in pelvic organ prolapse and robotic/laparoscopic-assisted sacrocolpopexy who does not have any scientific, financial, or other conflict of interest related to the study and who is not responsible for patient care at any of the participating sites. Safety will be formerly monitored by the study team and the independent Medical Monitor throughout the duration of the study, and the independent Medical Monitor will review safety data in aggregate every 6 months. The independent medical monitor and research team members will prepare a safety report for these regular reviews comprised of anticipated safety events and actions taken. The PI will contact the independent Medical Monitor for ad hoc reviews of any unanticipated safety events. The study protocol will be carried out in accordance with FDA guidelines and requirements. In the event of a serious adverse event during the study protocol, it will be reported immediately to the PI, the co-investigators, and the independent Medical Monitor. It will also be reported to the Northwell IRB for the study and to all members of the research team. With the approval of the participants and families, the information will be provided to other care providers as directed.

RISK ASSESSMENT

This study involves greater than minimal risk to the subjects. The primary concern is the development of numbness and bruising of injection site, severe allergic reaction and abnormal heart rhythm leading to death.

Subjects will be monitored throughout the study for these potential adverse events by phone call on the first postoperative day and then an office visit at two weeks post-surgery. The PI (or another designated Investigator in her absence) will be notified of any abnormal results so that the safety measures outlined below are implemented. The primary physician will also be notified of any abnormal results and any changes to the subject's care, and will also be provided with the test results. The potential risks and protections are as follows:

1. Abnormal Heart Rhythm

Monitoring: Electrocardiogram monitoring in the operating room where the Marcaine will be given and monitoring of vital signs in the operating room and after surgery is complete

Actions:

- o If severe abnormal heart rhythms at screening, subject will not be enrolled.
- o If severe abnormal heart rhythms at any study visit, subject will be taken off therapy, but will continue to be followed until end of study.
- o If the subject complains of symptoms concerning for abnormal heart rhythm (shortness of breath, chest pain, dizziness, abnormal heart beat), Abnormal heart rhythm will be checked in addition to any other clinical testing requested by primary physician.

2. Severe allergic reaction:

Monitoring: vital sign monitoring and patient monitoring before, during and after surgery

Actions:

- o If patient has an allergy to local numbing medication at screening, subject will not be enrolled.
- o If severe allergic reaction at any study visit, Marcaine (generic name: Bupivacaine) will not be furthermore given and the patient will be followed for two weeks post procedure.
- o If the subject complains of symptoms concerning for severe allergic reaction (chest pain, shortness of breath, rashes), Severe allergic reaction will be checked in addition to any other clinical testing requested by primary physician.

3. Methemoglobinemia

- Monitoring: oxygen status and any skin discoloration will be monitored in the operating room after injection has been given and after surgery
- Actions:
 - Immediate discontinuation of bupivacaine injection
 - Depending on the severity of the signs and symptoms, patients may respond to supportive care (oxygen, continued ventilation, and hydration)
 - A more severe clinical presentation may require treatment with methylene blue, exchange transfusion or hyperbaric oxygen.

